Only subjects who discontinue treatment with olaparib before end of Treatment Phase on study will be followed for 28 days after discontinuation of study drug or until the start of alternate treatment intervention, whichever is earlier. A telephone follow-up will be conducted 28 days after the EOT Visit. This will be considered as End-of-Study visit. Every effort should be made to conduct the telephone End-of-Study Visit before the subject starts subsequent treatment. For Follow – Up Phase visit, a window of \pm 3 days will be allowed.

Table 1 Study of Assessments

Study Phase	Screening Phase ^(a)	Treatment Phase					Follow-up Phase						
		On Treatment			EOT	EOS							
Cycle	1	2	3	4	5- 7	8	9						
Visit No.	1	2	3	4	5- 7	8	9						
Study Days	-6 to 0	1 (± 3 days)	15 (± 3 days)	29 (± 3 days)	57, 85 & 141 (± 3 days)	182 (± 3 days)	28 days post-EOT (± 3 days)						
Screening/Enrolment visit													
Informed consent ^(b)	Subjects must sign the informed consent form before any study-specific procedures are performed.												
Eligibility criteria	X												
Demographics/ Review medical history (including all treatments for ovarian cancer/breast cancer)	X												
WHO Performance Status	X			X	X	X	X						
General physical examination	X	Targeted physical exam (based on symptoms)											
Prior concomitant medication recording	Continuous from time of ICF until 28 days after last olaparib dose in treatment phase.												
Study drug administration													
Olaparib dosing	The recommended dose is 300 mg (150 mg X 2 tablets) twice a day												
Disease evaluations (disease characteristics will be performed as per routine clinical practice)													
Disease characteristics assessment	X			X	X								
Tumor imaging	X					X							

Study Phase	Screening Phase ^(b)	Treatment Phase					Follow-up Phase
		On Treatment			EOT	EOS	
Visit No.	1	2	3	4	5-7	8	9
Study Days	-6 to 0	1	15 (± 3 days)	29 (± 3 days)	57, 85 & 141 (± 3 days)	182 (± 3 days)	28 days post-EOT (± 3 days)
Safety evaluations							
Physical examination	X	Symptom-directed physical examination only					
Vital sign parameters	X	X			X	X	
ECG	X	Performed if clinically indicated					
Adverse event monitoring	Continuous from time of ICF until 28 days after last olaparib dose in Treatment Phase and Follow-up Phase if eligible.						
Haematology & Biochemistry ^[c]	X	X	X	X	X	X	X
Hepatitis B and C	X						
Pregnancy Test	X	X	X	X	X	X	X
PT/INR	X	X	X	X	X	X	X

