4. STUDY DESIGN

4.1 Overall design

This is a prospective, single - arm, multicentre, interventional phase – IV trial investigating the safety of olaparib in Indian adult subjects receiving olaparib as per the local approved prescribing information. The investigator will be trained on the locally approved prescribing information before the enrolment of the first subject at their site to ensure compliant and proper dosing of the study drug.

The decision of subjects to participate in this study must not, in any way, impact upon the standard of care that they are receiving or any benefits to which they are otherwise entitled. Prior to data collection, all subjects must sign an informed consent form (ICF) allowing data collection and source data verification in accordance with local requirements and sponsor policy. Subjects who are prescribed olaparib by an independent clinical judgement of investigator in his/her routine practice based on locally approved prescribing information will be eligible for screening under this study. To enrol approximately 200 subjects (160 patients to be enrolled in the ovarian cancer indication and 40 from the breast cancer indication), it is expected that approximately 225 subjects (180 patients with ovarian and 45 patients with breast cancer) will be screened.

Subjects will be monitored throughout the study period for AEs of olaparib.

Subject participation will include a Screening/Enrolment Phase, a Treatment Phase, and a Follow-up Phase. The Screening/Enrolment Phase will be up to 7 days prior to Day 1. The Treatment Phase will extend from Day 1 to Day 182; or until study drug discontinuation due to either disease progression or unacceptable toxicity; or other reasons as listed in Drug Discontinuation Section, whichever occurs first. The Follow-up Phase will begin once a subject discontinues study drug during Treatment Phase, and will continue until 28 days after last dose, death, loss to follow - up, consent withdrawal for study participation, or study end, whichever occurs first (see section 7). Subjects who are observed to continue to receive clinical benefit from olaparib at end of Treatment

Phase (as defined in SoA) will continue treatment in Extension Phase (defined in section 6.7) as long-term clinical benefit is observed or until the investigator decides it is not in the best interest of the subject to continue olaparib treatment.

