Safety will be evaluated throughout the evaluation phase and during the follow - up of subjects who discontinue treatment before end of Treatment Phase by physical exams including vital signs, AE/SAE monitoring, laboratory evaluations and recording of concomitant medications. The sponsor shall provide the laboratory investigations for safety evaluation including haematology and biochemistry as mentioned in the Time and Events Schedule to monitor the safety throughout the study period. A window period of +/- 3 days will be allowed for visits 3 – 9.

Screening Phase (Visit 1)

Subjects, or their legally acceptable representative, will provide written informed consent before any trial-specific procedures are performed. During the Screening Phase, eligibility criteria will be reviewed, and a complete clinical evaluation will be performed as specified in the Time and Events Schedule. Screening procedures will be performed within 7 days before Day 1 of therapy with olaparib. All baseline disease characteristics will be captured based on the evaluations as performed as a part of routine clinical practice in the enrolment hospital. The documented tests that are required before consideration of subject for olaparib treatment based on the local prescribing information by investigator must have been performed within 7 days before Day 1.

Treatment Phase (Visit 2-7)

The Treatment Phase will extend from Day 1 to Day 182; or until study drug discontinuation due to either disease progression or unacceptable toxicity; or other reasons whichever occurs first, as listed in the Drug Discontinuation Section. Details of the procedures performed during the Treatment Phase are outlined in the Time and Events Schedule. Subjects will be closely monitored for AEs and other safety evaluations including laboratory investigations and concomitant medications. If disease progression is diagnosed before Day 182, then the subject will discontinue study drug with completion of the End-of-Treatment Visit on the day of progression and will enter the Follow-up Phase.

End-Of-Treatment Visit (EOT; Visit 8)

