An End-of-Treatment Visit is to be scheduled on Day 182 of the study drug administration. In a case where subject discontinues the study treatment for any reason listed in Drug Discontinuation Section before Day 182, the last visit of the subject will be considered as End-of-treatment Visit. Every effort should be made to conduct the telephonic End-of-Study Visit before the subject starts subsequent treatment.

Follow - Up Phase (End – Of – Study; Visit 9)

Only subjects who discontinue treatment with olaparib before end of Treatment Phase on study will be followed for 28 days after discontinuation of study drug or until the start of alternate treatment intervention, whichever is earlier. A telephone follow-up will be conducted 28 days after the EOT Visit. This will be considered as End-of-Study visit. Every effort should be made to conduct the telephone End-of-Study Visit before the subject starts subsequent treatment.

For an overview of the study design see Figure 1, Section 1.3. For details on treatments given during the study, see Section 6.1 Treatments Administered.

For details on what is included in the study endpoints, see Section 3 Objectives and Endpoints.

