8.3.2 Time - period and frequency for collecting AE and SAE information

Adverse Events will be collected continuously from time of ICF until 28 days after last olaparib dose in Treatment Phase and Follow-up Phase.

All SAEs will be recorded and reported to the sponsor or designee within 24 hours, as indicated in Appendix B. The investigator will submit any updated SAE data to the sponsor within 24 hours of it being available.

Investigators are not obligated to actively seek AE or SAE in former study subjects. However, if the investigator learns of any SAE, including a death, at any time after a subject's last visit and he/she considers the event to be reasonably related to the Study treatment or study participation, the investigator may notify the sponsor.

The method of recording, evaluating, and assessing causality of AE and SAE and the procedures for completing and transmitting SAE reports are provided in Appendix B.

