9.4.2 Safety analyses

Safety analyses will be performed on the safety analysis set as described above in section 9.3.

Data will be summarized using descriptive statistics. Continuous variables will be summarized using the number of observations, mean, standard deviation (SD), median, and range as appropriate. Categorical values will be summarized using the number of observations and percentages as appropriate.

AEs (both in terms of MedDRA preferred terms and CTCAE grade) will be listed individually by subject. Any AE occurring before treatment with olaparib will be included in the data listings but will not be included in the summary tables of AEs.

Any AE occurring within 28 days of discontinuation of study drug (i.e., the last dose of olaparib) will be included in the AE summaries. Any events in this period that occur after a subject has received further therapy for cancer (following discontinuation of olaparib) will be flagged in the data listings.

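### Sections 1.1 and 4.1 end follow-up of early stoppers when new treatment starts, but 8.3.2 and 9.4.2 need their adverse events to 28 days after the last dose

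*Protocol*

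**What the plan says.** **Rule that stops at new treatment.** The Follow-Up Phase text appears in both 1.1 and 4.1. It says early stoppers "will be followed for 28 days after discontinuation of study drug or until the start of alternate treatment intervention, whichever is earlier". Both sections then schedule a telephone End-of-Study call 28 days after the End-of-Treatment visit and ask sites to try to hold it before the next treatment begins. Section 4.1 also says that safety is evaluated "during the follow - up of subjects who discontinue treatment before end of Treatment Phase by physical exams including vital signs, AE/SAE monitoring", so AE monitoring is part of this follow-up.

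**Rules that do not stop at new treatment.**
- The design paragraph of 4.1 says the Follow-up Phase "will continue until 28 days after last dose, death, loss to follow - up, consent withdrawal for study participation, or study end", whichever comes first. New therapy is not in that list.
- Section 8.3.2: "Adverse Events will be collected continuously from time of ICF until 28 days after last olaparib dose in Treatment Phase and Follow-up Phase".
- AE row of the Schedule of Activities: "Continuous from time of ICF until 28 days after last olaparib dose in Treatment Phase and Follow-up Phase if eligible". The last two words are not defined.
- Section 9.4.2: "Any AE occurring within 28 days of discontinuation of study drug (i.e., the last dose of olaparib) will be included in the AE summaries". It then says that "Any events in this period that occur after a subject has received further therapy for cancer" will be flagged in the listings.

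**Day-182 completers.** Section 1.1 says "Only subjects who discontinue treatment with olaparib before end of Treatment Phase on study will be followed", which leaves completers out. Section 6.7 provides no active AE monitoring for those who continue on compassionate supply. Section 7.3, on vital status, places the End-of-Study visit at Day 182 or 28 days after withdrawal, whereas the Schedule of Activities places it 28 days after End of Treatment.

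**The concern.** AE and serious AE counts are the primary endpoint (Sections 3 and 9.1). For a subject who starts another cancer treatment within 28 days of the last olaparib dose, the protocol gives two different ends to observation. The shorter one drops events that the analysis section says will be counted.

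The situation is foreseeable. Section 7.1.2 says permanent discontinuers should receive local standard-of-care therapy. These are also the subjects who stopped because of progression or toxicity.

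If sites read the text differently, early stoppers are observed for different lengths of time from site to site. Measured against the counting rule in 9.4.2, the shorter reading can only lose events. Only the protocol is at hand here, but no analysis plan could restore events that were never recorded.

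**Working it through.** **Step 1: set the rules side by side.** Take an early stopper who starts new therapy on day *t* after the last dose, with *t* < 28.

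| Place | End of observation | Days *t* to 28 covered? |
|---|---|---|
| 1.1 and 4.1, Follow-Up Phase | day *t* | no |
| 4.1, design paragraph | day 28 | yes |
| 8.3.2 | day 28 | yes |
| Schedule of Activities, AE row | day 28, with an undefined qualifier | yes on its face |
| 9.4.2 | day 28, later events flagged | yes, explicitly |

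Section 4.1 therefore contradicts itself as well as 8.3.2 and 9.4.2. In 8.3.2, coverage after new therapy follows from an unqualified window. Only 9.4.2 addresses new therapy directly.

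Days lost = 28 − *t*. For *t* = 0, 7, 14 and 21 this is 28, 21, 14 and 7 days, or 100%, 75%, 50% and 25% of the window.

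**Step 2: how events go unrecorded.** No sentence tells sites to stop recording AEs. The likely route is that the End-of-Study call is brought forward to precede the next treatment. Section 4.4 treats that visit as completion, and 8.3.2 does not oblige investigators to look for AEs in former subjects. The Schedule of Activities sets the call at 28 days post-EOT (± 3 days), and nothing says whether an earlier call closes AE collection.

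**Step 3: the plan's own figure.** Section 9.2 assumes 40% incidence of grade 3 or higher AEs, a 7-point margin and a 95% interval. n = 1.96² × 0.4 × 0.6 / 0.07² = 188.2, rounded up to 189, which agrees with the stated figure of about 190. The conflict does not change this number; it only supplies a yardstick.

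**Step 4: illustrative size.** The protocol gives no early-stop rate and no rate of switching within 28 days. The following are assumptions:
- 40% is the risk over 182 days, at a constant hazard that persists after olaparib stops;
- *s* = share stopping early, 10% to 40%;
- *w* = share of those switching at once, with nothing recorded afterwards, 25% to 100%;
- *d* = stop day, 29 to 141.

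The range for *s* is compatible with the protocol's own median progression-free survival figures. With exponential times, and 182 days taken as 5.98 months, the share progressed or dead by Day 182 is 1 − 0.5^(5.98/19.1) = 20%, 1 − 0.5^(5.98/8.4) = 39% and 1 − 0.5^(5.98/7) = 45%. Weighted 160:40 for ovarian and breast, this is about 25% to 40%.

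28-day risk in an event-free subject = 1 − 0.6^(28/182) = 0.0756.

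Loss in pooled incidence = *s* × *w* × 0.6^(*d*/182) × 0.0756.

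| *s* | *w* | *d* | Loss (points) | Subjects of 200 |
|---|---|---|---|---|
| 0.10 | 0.25 | 141 | 0.13 | 0.25 |
| 0.25 | 0.50 | 91 | 0.73 | 1.5 |
| 0.40 | 1.00 | 29 | 2.79 | 5.6 |

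All three are below the 7-point margin.

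**The case against.** The strongest reply is that the AE-specific text points one way. Section 8.3.2 and the AE row give 28 days. Section 7.1.2 says participation and data collection continue after discontinuation for any reason, and requires a modified follow-up if in-person visits are refused. The 28-day call is scheduled without condition, and its open question about health problems since the last visit (8.3.6) could pick up events after a switch. On this view, one general follow-up sentence, repeated in 1.1 and 4.1, is the outlier and the loss of events is inferred.

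Part of this stands. The loss is a risk, not a certainty, and it arises mainly where the call is brought forward and the subject is closed out. The number affected is unknown, and the illustration should carry no weight in judging seriousness.

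The contradiction remains. No text gives 8.3.2 precedence, and Section 8 makes adherence to the design requirements and the Schedule of Activities mandatory. Section 7.1.2 foresees both new therapy and continued collection, so it adds to the conflict with 1.1 and 4.1.

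It can also be said that events after a switch may belong to the next therapy, so that counting them inflates the incidence attributed to olaparib. That is true of attribution, but 9.4.2 has already chosen to count and flag them, and they must be recorded for that to be possible.

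The point on Day-182 completers is weaker. Section 7.3 concerns vital status, and the text could be read as ending their AE monitoring at Day 182. It is a secondary ambiguity in a different group of subjects.

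**Conclusion.** The concern holds: the protocol is wrong as written and should be corrected. The Follow-Up Phase text in 1.1 and 4.1 conflicts with the design paragraph of 4.1, with 8.3.2, with the AE row and with 9.4.2. Confidence in the textual conflict is high. The actual loss of events cannot be estimated from the protocol.

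What the text itself fixes is the range for one subject: 0 post-dose days of follow-up under one rule against 28 under the other for someone who switches at once. The pooled effect of 0.1 to 2.8 points rests wholly on the assumptions in the working and concerns grade 3 or higher events only. Its upper end needs 40% of subjects to stop at Day 29, all to switch at once, and nothing to be recorded afterwards. The defect is incomplete and possibly site-dependent collection of the primary endpoint, not a failed precision target.

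**What to change.** 1. In 1.1 and 4.1, remove the start of alternate treatment as a limit on AE collection. State that AEs in early stoppers are collected to 28 days after the last olaparib dose whether or not new cancer therapy has begun, and are flagged as 9.4.2 already provides.
2. State that an End-of-Study call brought forward because of new therapy does not close AE collection before day 28.
3. State one AE cut-off for Day-182 completers and use it in 1.1, 4.1, 6.7, 7.3, 8.3.2, 9.4.2 and the Schedule of Activities, defining or deleting the qualifier in the AE row.

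**Cost.** For early stoppers this is wording plus a few more AEs to record, some due to the next therapy; their 28-day call is already scheduled, although one brought forward would need a later check on AEs to day 28. If the cut-off chosen for completers is 28 days, each needs one further contact. No dose or treatment rule changes.

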4.2 Scientific rationale for study design

This is a phase IV single arm study being conducted to fulfil the regulatory requirement for the conditional approval of Olaparib in India. The safety results need to be submitted to the health authorities within 2 years of the market authorization which makes it practically impossible to include data on efficacy considering the median PFS in SOLO – 2 was 19.1 months and 8.4 months for Study 19 (Ledermann JA , et al, 2016; Pujade-Lauraine et al., 2017).

4.3 Justification for dose

This study's Inclusion criteria specifies that patients fitting into the Indian Approved Prescribing information will be included.

4.4 End of study definition

The end of study is defined as the last expected visit/contact of the last subject undergoing the study.

A subject is considered to have completed the study when he/she has completed his/her end of study visit as per the SoA in Section 1.1.

See Appendix A 6 for guidelines for the dissemination of study results.

5. STUDY POPULATION

Prospective approval of protocol deviations to recruitment and enrolment criteria, also known as protocol waivers or exemptions, is not permitted.

Each subject should meet all the inclusion criteria and none of the exclusion criteria for this study in order to assigned/randomised to a study intervention. Under no circumstances can there be exceptions to this rule. Subjects who do not meet the entry requirements are screen failures, refer to section 5.4.

In this protocol, "enrolled" subjects are defined as those who sign informed consent.

For procedures for withdrawal of incorrectly enrolled subjects see Section 7.3.

5.1 Inclusion criteria

Subjects are eligible to be included in the study only if all of the following inclusion criteria and none of the exclusion criteria apply:

Informed consent

1. Capable of giving signed informed consent which includes compliance with the requirements and restrictions listed in the informed consent form (ICF) and in this protocol.
2. *Provision of signed and dated, written informed consent form prior to any mandatory study specific procedures, sampling, and analyses.*

The ICF process is described in Appendix A 3.

Age

3. *Subjects ≥ 18 years of age*

Type of subject and disease characteristics

4. *Subjects receiving olaparib for the following indications in ovarian cancer:*

for the maintenance treatment of adult subjects with recurrent epithelial ovarian, fallopian tube or primary peritoneal cancer, who are in a complete or partial response to platinum-based chemotherapy

5. *Subjects receiving olaparib for the following indication in breast cancer:*

in subjects with deleterious or suspected deleterious gBRCAm, HER2-negative metastatic breast cancer who have previously been treated with chemotherapy in the neoadjuvant, adjuvant or metastatic setting. Subjects with HR-positive breast cancer should have been treated with a prior endocrine therapy or be considered inappropriate for endocrine treatment

Sex

6. *Only Females will be recruited*

Reproduction

7. *Negative pregnancy test (urine or serum) for female subjects of childbearing potential at least 72 hours prior to beginning treatment.*

8. *Female subjects of childbearing potential must be willing to use an adequate method of contraception for the course of the study and through 120 days after the last dose of trial treatment.*

Organ function

9. *Have adequate organ function as defined in Table X. Specimens must be collected within 10 days prior to the start of trial treatment.*

Table X Adequate Organ Function Laboratory Values

System	Laboratory value
Hematological	
Absolute neutrophil count (ANC)	$\geq 1500/\mu\text{L}$
Platelets	$\geq 100,000/\mu\text{L}$
Hemoglobin	$\geq 9.0 \text{ g/dL or } \geq 5.6 \text{ mmol/L}$
Renal	
Creatinine OR Measured or calculated creatinine clearance (GFR can also be used in place of creatinine or CrCl)	$\leq 1.5 \times \text{ULN OR}$ $\geq 30 \text{ mL/min for subject with creatinine levels } > 1.5 \times \text{institutional ULN}$
Hepatic	
Total bilirubin	$\leq 1.5 \times \text{ULN OR direct bilirubin } \leq \text{ULN for subjects with total bilirubin levels } > 1.5 \times \text{ULN}$
AST (SGOT) and ALT (SGPT)	$\leq 2.5 \times \text{ULN OR}$ $\leq 5 \times \text{ULN for subjects with liver metastases}$
Coagulation	
International normalized ratio (INR) or prothrombin time (PT)	$\leq 1.5 \times \text{ULN unless subject is receiving anticoagulant therapy as long as PT or PTT is within therapeutic range of intended use of anticoagulants}$
Activated partial thromboplastin time (aPTT)	

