1. PROTOCOL SUMMARY

1.1 Schedule of Activities (SoA)

Screening Phase (Visit 1)

Subjects, or their legally acceptable representative, will provide written informed consent before any trial-specific procedures are performed. During the Screening Phase, eligibility criteria will be reviewed, and a complete clinical evaluation will be performed as specified in the Time and Events Schedule. Screening procedures will be performed within 7 days before Day 1 of therapy with olaparib. All baseline disease characteristics will be captured based on the evaluations as performed as a part of routine clinical practice in the enrolment hospital. The documented tests that are required before consideration of subject for olaparib treatment based on the local prescribing information by investigator must have been performed within 7 days before Day 1.

Treatment Phase (Visit 2-7)

The Treatment Phase will extend from Day 1 to Day 182; or until study drug discontinuation due to either disease progression or unacceptable toxicity; or other reasons whichever occurs first, as listed in the Drug Discontinuation Section. Details of the procedures performed during the Treatment Phase are outlined in the Time and Events Schedule. Subjects will be closely monitored for AEs and other safety evaluations including laboratory investigations and concomitant medications. If disease progression is diagnosed before Day 182, then the subject will discontinue study drug with completion of the End-of-Treatment Visit on the day of progression and will enter the Follow-up Phase. For visit 3 – 7, a window of \pm 3 days will be allowed per visit.

End-Of-Treatment Visit (EOT; Visit 8)

An End-of-Treatment Visit is to be scheduled on Day 182 of the study drug administration. In a case where subject discontinues the study treatment for any reason listed in Drug Discontinuation Section before Day 182, the last visit of the subject will be considered as End-of-treatment Visit. Every effort should be made to conduct the telephonic End-of-Study Visit before the subject starts subsequent treatment. For end – of – treatment visit, a window of \pm 3 days will be allowed.

Follow - Up Phase (End – Of – Study; Visit 9)

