Comprehensive serum chemistry panel	X	X	X	X	X	X	X
Urinalysis	X	X	X	X	X	X	X

Footnotes:

EOT = End-of-Treatment. EOS = End-of-Study. ICF = informed consent form.

- The Screening Phase begins when the first screening procedure is conducted. Screening tests should be performed within 7 days of Day 1 except for disease evaluations (performed as routine clinical practice).
- Must be signed before first study-related activity.
- Haematology and biochemistry as described in the Safety Evaluations section

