5.2 Exclusion criteria

Medical conditions

1. Subjects with either the history of hypersensitivity to excipients of the study drug or to drugs with a similar chemical structure or class to the study drug OR
2. pregnant and/or lactating women OR
3. Patients with a previously or currently diagnosed MDS/ AML or pneumonitis OR
4. Patients who have not recovered sufficiently from prior surgery or anticancer treatment OR
5. Patients who have known history of hepatitis B or hepatitis C OR
6. Patients with active infection such as TB

Prior/concurrent clinical study experience

7. Participation in another clinical study with a study drug administered in the last 3 months

Other exclusions

8. Judgment by the investigator that the subject should not participate in the study if the subject is unlikely to comply with study procedures, restrictions and requirements.
9. Previous enrolment in the present study.

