7.1 Discontinuation of study treatment

Subjects may be discontinued from olaparib in the following situations. Note that discontinuation from study treatment is NOT the same thing as a complete withdrawal from the study

- Disease Progression: Disease progression can be considered as a worsening of a subject's condition attributable to the disease for which the study drug is being studied. It may be an increase in the severity of the disease under study (DUS) and/or increases in the signs and symptoms of the cancer. The development of new, or progression of existing metastasis to the primary cancer under study should be considered as disease progression and not an AE (if the progression was 'as expected'). Events, which are unequivocally due to disease progression, should not be reported as an AE during the study. All the events occurring at the Indian sites that meet the criteria for seriousness will be reported expeditiously as SAEs per local regulatory requirements to the Indian regulatory authority and the concerned ethics committees. In this study, disease progression shall be determined by the investigator as per the guidelines currently being followed by the site for the indication in question. Progression of disease assessed radiographically should occur in comparison to baseline imaging obtained during screening.

- Adverse Event (including laboratory abnormality or intercurrent illness) which, in the opinion of the investigator, indicates that continued participation in the study is not in the best interest of the subject
- The subject (or the subject's legally acceptable representative) withdraws consent for administration of study drug
- ILD/Pneumonitis
- Acute myeloid leukemia/Myelodysplastic syndrome or other de novo malignancy requiring active treatment
- Pregnancy
- Any adverse event deemed to be related to olaparib that requires a dose hold of more than 21 days will result in permanent discontinuation of olaparib.
- Grade 3 or higher adverse reaction that does not improve to Grade 0-2 after withholding for up to 3 weeks
- Severe non-compliance with the Clinical Study Protocol
- The patient has a confirmed positive serum pregnancy test

See the SoA for data to be collected at the time of treatment discontinuation and follow-up and for any further evaluations that need to be completed.

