8.4.2.1 Maternal exposure

If a subject becomes pregnant during the course of the study, the study drug olaparib should be discontinued immediately.

Pregnancy itself is not regarded as an adverse event unless there is a suspicion that the study drug under study may have interfered with the effectiveness of a contraceptive medication. Congenital abnormalities/birth defects and spontaneous miscarriages should be reported and handled as SAEs. Elective abortions without complications should not be handled as AEs. The outcome of all pregnancies (spontaneous miscarriage, elective termination, ectopic pregnancy, normal birth or congenital abnormality) should be followed up and documented even if the subject was discontinued from the study.

If any pregnancy occurs during the course of the study, then the Investigator or other site personnel informs the appropriate AstraZeneca representatives within 1 day i.e., immediately but **no later than 24 hours** of when he or she becomes aware of it.

The designated AstraZeneca representative works with the Investigator to ensure that all relevant information is provided to the AstraZeneca Patient Safety data entry site within 1 or 5 calendar days for SAEs (see Section 9.2.5) and within 30 days for all other pregnancies.

The same timelines apply when outcome information is available.

<<When the CRF module is used include the following: The PREGREP module in the CRF is used to report the pregnancy and the PREGOUT is used to report the outcome of the pregnancy.>>

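### Inclusion criterion 7 sets 72 hours as the minimum age of the qualifying pregnancy test instead of the maximum, so tests on Day -1, Day 0 and Day 1 cannot satisfy it

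*Protocol*

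**What the plan says.** **Entry criterion.** Protocol Section 5.1, inclusion criterion 7, requires a negative urine or serum pregnancy test in women of childbearing potential, timed "at least 72 hours prior to beginning treatment". It gives no upper limit on the age of the test.

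**Schedule.** Section 1.1 states: "Screening procedures will be performed within 7 days before Day 1 of therapy with olaparib". Section 4.1 says the same, and the Table 1 footnote agrees: "Screening tests should be performed within 7 days of Day 1 except for disease evaluations". Table 1 numbers the screening days -6 to 0, followed by Day 1. Its row "Pregnancy Test" is marked at screening, on Day 1 and at every later visit.

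**Strictness.** Section 5 says of the entry criteria: "Under no circumstances can there be exceptions to this rule". Section 5.4 does not allow screen failures to be rescreened.

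**Other pregnancy safeguards.** Exclusion criterion 2 in Section 5.2 covers "pregnant and/or lactating women OR" and names no test and no timing. Section 7.1 lists as a reason to stop treatment: "The patient has a confirmed positive serum pregnancy test". Section 8.4.2.1 adds: "If a subject becomes pregnant during the course of the study, the study drug olaparib should be discontinued immediately".

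**Related window.** Inclusion criterion 9 accepts organ-function specimens up to 10 days before treatment starts, against 7 days in Sections 1.1 and 4.1 and the Table 1 footnote.

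**The concern.** A pregnancy test at entry is there to show that a woman is not pregnant when she takes her first dose, so a recent test is worth more than an older one. Criterion 7 reverses that order: the older result meets the rule and the results nearest to dosing do not. The Day 1 test in Table 1 is scheduled, but it cannot count towards the criterion.

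Because Section 5 rules out waivers, a site cannot simply read the criterion as it was probably meant. If a woman's test falls on Day -1 or Day 0 and she is dosed on Day 1, the schedule has been followed and criterion 7 has been failed. The site must then delay the first dose, declare a screen failure or record an eligibility deviation. Delaying makes the qualifying result older.

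Criterion 7 is also the only entry criterion that specifies a pregnancy test, so its time limit should be the one that protects first dose.

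**Working it through.** **What the wording means.** The protocol uses its two time phrases consistently, which leaves little room to read criterion 7 as a maximum.

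| Phrase | Where | Sense |
|---|---|---|
| *within* 10 days | 5.1, criterion 9 (organ-function specimens) | maximum age |
| *within* 7 days | 8.2.3 (ECG before treatment) | maximum age |
| *at least* 4 weeks | 6.5.1 (start of bisphosphonates, denosumab or corticosteroids before treatment) | minimum interval |
| *at least* 3 days | 8.4.6.3 (stopping before planned surgery) | minimum interval |
| *at least* 72 hours | 5.1, criterion 7 | minimum interval |

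Nothing in the protocol says that a 72-hour maximum is meant.

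**Inputs.** Screening days are -6 to 0, with a further pregnancy test on Day 1 (Table 1). First dose is on Day 1. The threshold is 72 hours (criterion 7).

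**Formula.** The day numbering includes a Day 0. A test on Day *d* at the same clock time as the first dose therefore has age (1 − *d*) × 24 hours. If the clock times differ, the age lies strictly between that value minus 24 and that value plus 24 hours, and cannot be below 0.

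| Test day | Age at same clock time (h) | Range over clock times (h) | As written (≥ 72 h) | If reversed (≤ 72 h) |
|---|---|---|---|---|
| -6 | 168 | 144–192 | qualifies | fails |
| -5 | 144 | 120–168 | qualifies | fails |
| -4 | 120 | 96–144 | qualifies | fails |
| -3 | 96 | 72–120 | qualifies | fails |
| -2 | 72 | 48–96 | depends on clock time | depends on clock time |
| -1 | 48 | 24–72 | fails | qualifies |
| 0 | 24 | 0–48 | fails | qualifies |
| 1 (before dose) | 0 | 0–24 | fails | qualifies |

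The ranges are open intervals. A Day -1 test therefore stays short of 72 hours and a Day -3 test exceeds it.

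**Result.** At equal clock times, qualifying tests as written are those on Days -6 to -2, aged 72 to 168 hours. With the limit reversed they are those on Days -2 to 1, aged 0 to 72 hours. The two sets share only Day -2.

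**Criterion 9.** Specimens aged 8, 9 or 10 days meet criterion 9 but fall outside the 7-day screening window. The windows are nested, so any specimen aged 7 days or less satisfies both.

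**The case against.** The strongest reply is that the protocol as a whole already protects first dose. Screening is capped at 7 days, so criterion 7 cannot admit a very old test. Table 1 repeats the test on Day 1. Exclusion 2 bars pregnant women whatever the test timing, and it cannot be waived either. Section 8.4.2 foresees a pregnancy found before any drug is taken. An earlier eligibility test plus a Day 1 repeat arguably covers first dose at least as well as a single test within 72 hours.

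The criterion can also be met without excluding anyone: test on Days -6 to -3, or start dosing at least 72 hours after a late test. Criterion and schedule do not contradict each other. On this view the point is a drafting slip.

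Most of this stands as a limit on the harm, but it does not correct the criterion:

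- No section requires the Day 1 result to be read as negative before the first dose.
- Exclusion 2 depends on a pregnancy being known and prescribes no test.
- The stopping rules in Sections 7.1 and 8.4.2.1 act only once dosing has begun.
- The scheduling remedy works only by making the qualifying test older.

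A drafting slip is the likeliest explanation. Under a no-exceptions rule, however, the slip is what sites must apply.

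On criterion 9 the reply is largely right. Section 8 already limits routine results used for screening to the time frame in the schedule, so the mismatch can at most produce a minor timing deviation.

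**Conclusion.** The concern holds. Criterion 7 as written excludes every pregnancy test on Day -1, Day 0 and Day 1. It accepts tests about 3 to 7 days old, where a correctly directed limit would accept tests 0 to 72 hours old. Protection close to first dose comes from the Day 1 test and exclusion 2, not from the criterion written for that purpose.

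This rests on first dose being on Day 1, on Table 1's day numbering with a Day 0, and on reading the criterion literally, as Section 5 demands. The 0-to-72-hour figure describes the proposed wording; the protocol does not state it.

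The wording alone is not claimed to lead to a pregnant woman being dosed. Only women of childbearing potential are affected, and their number cannot be derived from the protocol. Sample size, endpoint and analysis do not change. The correction should be made because a non-waivable safety criterion runs in the wrong direction and is easy to put right. The criterion 9 mismatch is a harmonisation note only.

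**What to change.** - **Criterion 7:** require the negative test *within 72 hours before the first dose*. Add one sentence that the Day 1 test already in Table 1, read as negative before the first dose, satisfies the criterion.
- **Criterion 9 (minor):** change 10 days to 7 days, to match Sections 1.1 and 4.1 and the Table 1 footnote.

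The cost is a wording change to two criteria and one added sentence. No new pregnancy test is needed. A few laboratory tests aged 8 to 10 days would have to be repeated, which the schedule already calls for.
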